12.1 Study Database

PrismRA arm:

Data will be collected into the study database through a secure, electronic database capture (EDC) system or an electronic data transfer via an encrypted secure sockets layer protocol to the Scipher Medicine data lake.

Electronic case report forms will be maintained in the EDC, and all relevant observations and data related to the protocol-defined assessments will be recorded. This will include, at minimum, demographics, medical history, physical examinations, laboratory results, clinical assessments, treatment information, and patient reported outcomes.

Prior to recording data in the paper CRF, Investigators and site staff will be trained on how to accurately capture data. Trained and qualified Investigators and site staff will be responsible for recording data in the paper CRFs.

The study database will be password protected and access will be provided only to trained and authorized personnel. Data collected into the study database may include protected health information (PHI). This PHI will not be shared beyond the Sponsor/designee or site without specific institutional review board (IRB) approval and additional patient consent.

External control arm:

An analytic dataset of eligible RA patients, built upon the underlying OM1 enterprise data warehouse, will be created for this study. The OM1 data warehouse is built on OM1 Origin Plus™, a scalable cloud computing platform with high availability and dependability. The analytic dataset will contain data ingested from multiple sources in multiple formats and will serve as a repository of centralized, standardized, normalized, and integrated data from the different sources. Where necessary and possible, data from disparate sources will be linked with other data that are attributed to a common patient creating a longitudinal record. Data will be standardized and normalized as necessary, for example, classifications of text documents such as lab reports and pathology reports. A detailed technical data management plan describing processes for transferring data, managing data quality, and maintaining data security will be developed and implemented for the study.

12.2 Inspection of Records

PrismRA arm:

Sponsor or its designee will be allowed to conduct site visits either remotely or at the Investigator's clinical research facilities for the purpose of monitoring any aspect of the study, as

applicable. The Investigator agrees to allow the Sponsor or its designee to inspect the facilities, patient medical records, source documents, and other records relative to study conduct. Source documents containing PHI will be protected and transferred to the Sponsor or its designee via a secure, HIPAA compliant portal. Study records containing patient health information will be maintained in a confidential manner.

12.3 Retention of Records

PrismRA arm:

All primary data collected as a result of the original observations and activities of the study and that are necessary for the reconstruction and evaluation of any study report will be retained in a secure archive at the study site for a period not less than 6 years after the last approval of a marketing application in an International Council for Harmonization (ICH) region, and until there are no pending or contemplated marketing applications in an ICH region, or until at least 6 years have lapsed since the formal discontinuation of the clinical development of the investigational product. All country and region-specific requirements that may be more stringent than the 6 years included in ICH shall be followed.

The site will maintain an Investigator Site File (ISF), which will be maintained at the study site and in accordance with local and Federal regulations, as applicable. The site must keep this ISF current and available for review by the Sponsor, IRB, and/or regulatory bodies.

External control arm:

Based on recommendations from International Society for Pharmacoepidemiology Guidelines for GPP, all analysis datasets used for the final analysis will be archived for at least five years after the delivery of the final tables to Scipher Medicine unless specific requests are made during the report process.

12.4 Confidentiality (PrismRA arm Only)

12.4.1 Confidentiality of Records

PrismRA arm:

All study sites, laboratories, and parties supporting this study must comply with HIPAA, where applicable. All data and records generated throughout this study will be kept confidential in accordance with local and Federal policies and HIPAA on patient privacy.

At consent, personal identifying information, including patient name, birth date, and contact information, will be collected and stored on a secure and HIPAA-compliant research database.

Following consent, each patient will be assigned a unique study identification number that will be used to track their de-identified data.

Records that may have patient identifying information will be kept confidential in accordance with applicable guidelines, regulations, and laws.

External control arm:

The study utilizes a de-identification and secure patient key software tool to create statistically de-identified data sets and to create de-identified keys for patients. The tool generates tokens based on a patient's primary information (first name, last name, date of birth, and gender) and all study analysis performed will use the statistically de-identified data. Only a few limited data set data elements, including dates of service and date of death, will be part of the study data set. All parties will ensure protection of patient personal data and will not include patient identifiable information on any study forms, reports, publications, or in any other disclosures, except where required by law.

The database is housed on a secure cloud computing platform on which all OM1 technical operations, data processing, and storage are conducted. The global infrastructure is designed and managed according to security best practices as well as a variety of security compliance standards making it one of the most secure computing infrastructures in the world. The system also meets the standards of the ICH E6 (R2) guideline regarding electronic study data handling and is available for audit upon request. Patient confidentiality will be strictly maintained.

12.4.2 Review of Records

Sponsor and/or its designee will review source documents (i.e., medical records, laboratory results) and data collected throughout the study. In addition, an auditor, IRB, FDA, or national or local regulatory authorities may access and review applicable source documents, records, and data. All patients will be notified of and consent to this possibility during the consenting process.

12.4.3 Study results

If any results of the study are published, the patient's identity will remain confidential.

12.4.4 Future Use of Data or Specimens

PrismRA arm:

Data collected throughout the study and subsequently de-identified will be used for future research and/or distributed to other investigators for future research.

PrismRA samples from patients processed at Scipher Medicine's CLIA-certified CAP-accredited laboratory will also be de-identified and used for future research and/or distributed to other investigators for future research. Future research will include extracting and sequencing DNA isolated from the blood samples, in addition to the RNA that is extracted and sequenced for PrismRA. Future research may also include discovering novel biomarkers for disease diagnosis, monitoring, or progression as well as discovering new disease mechanisms, therapeutic targets, and therapies for autoimmune disorders.

De-identified data may be stored indefinitely, and de-identified specimens may be stored for up to 10 years following study completion. The de-identified data and specimens may be shared with researchers/institutions outside of Scipher without additional informed consent from the subject or the legally authorized representative. This could include for-profit companies.

External control arm:

Patients in the external control arm are from the OM1 PremiOM RA dataset, owned and maintained by OM1. OM1 PremiOM RA data may be used for analyses in the future per agreement.

13 Ethics

13.1 Ethics Review

The protocol, ICF, and any advertisements must be approved or given a favorable opinion in writing by an IRB. The Investigator must submit written and dated verification of the IRB approval to Sponsor before he or she can enroll any patient into the study.

The Sponsor/designee or Investigator will inform the IRB of any amendment to the protocol in accordance with local requirements. The protocol must be re-approved by the IRB upon receipt of amendments and annually, if required per local and IRB regulations.

Initial IRB approval, and all materials approved by the IRB for this study including the patient consent form and recruitment materials must be maintained by the Investigator and made available for inspection.

13.2 Ethical Conduct of the Study

The Sponsor, Investigators, study staff and designees will conduct the study in accordance with the ethical principles that have their origin in the Declaration of Helsinki and are consistent with ICH, GCP, and other applicable local and federal laws, regulations, and guidelines.

14 Quality Control

14.1 Data Quality

PrismRA arm:

Site and data monitoring will occur in accordance with the clinical monitoring plan, if applicable. Data captured in the study database will be compared against the source data for completeness and accuracy. Discrepancies will be addressed and corrected, if required, by qualified site personnel.

eCRF data will also be routinely reviewed for timeliness, errors, accuracy, and omissions. Any data issues will be submitted to the site for further clarification. Qualified site personnel will address queries and correct data in the study database or paper source files.

14.2 Protocol Deviations

PrismRA arm:

Study sites and databases will be evaluated for protocol deviations.

At study completion, the number and type of protocol deviations will be analyzed by the study biostatistician to review the events by site to determine if the deviations could affect the integrity of the study data. The study biostatistician will report findings to the Sponsor.

15 Protocol revision history

Rev. #	Effective Date	Summary of Changes
3.0	20-Oct-2022	Change to an external control arm design and sample size adjustment.
2.0	04-Feb-2022	Change in study title, endpoints, clarification of study design, and general edits.
1.0	23-Jul-2021	Initial Release

16 References

5. Fleischmann R, van Adelsberg J, Lin Y, et al. Sarilumab and Nonbiologic Disease-Modifying Antirheumatic Drugs in Patients With Active Rheumatoid Arthritis and Inadequate Response or Intolerance to Tumor Necrosis Factor Inhibitors. *Arthritis Rheumatol* 2017; **69**(2): 277-90.

MI	Multiple Imputation
MID	Minimal Important Difference
MNAR	Missing Not at Random
MOA	Mechanism of Action
MTX	Methotrexate
NPI	National Provider Identifier
NSAIDs	Non-Steroidal Anti-Inflammatory Drug
PRO	Patient Reported Outcomes
PS	Propensity Score
PtGA	Patient Global Assessment
RA	Rheumatoid Arthritis
RAPID3	Routine Assessment of Patient Index Data 3
RDCI	Rheumatic Disease Comorbidity Index
RNA	Ribonucleic Acid
RWDC	Real-World Data Cloud
SAE	Serious Adverse Event
SAP	Statistical Analysis Plan
SD	Standard Deviation
SOC	Standard of Care
TB	Tuberculosis
TNFi	Tumor Necrosis Factor Inhibitor
tsDMARD	Targeted small molecule Synthetic Disease Modifying Anti-Rheumatic Drug
UADE	Unanticipated Adverse Device Effect
US	United States

1.0 OVERVIEW OF STUDY DESIGN

This is a two-arm, multi-center United States (U.S.)-based study with a prospective, non-blinded intervention arm (PrismRA arm) and an observational external control arm designed to demonstrate the clinical utility of the PrismRA test in routine clinical care. The study will compare outcomes for rheumatoid arthritis (RA) patients with moderate to high disease activity whose treatment is informed by PrismRA test results (PrismRA arm) to outcomes among RA patients who receive the standard of care (SOC) not informed by PrismRA results (external control arm). The study will be conducted using a modified intention-to-treat (ITT) principle.^[1] All eligible participants meeting inclusion and exclusion criteria *and* initiating the study treatment will be included.

PrismRA arm:

In this arm, all patients will be enrolled into the PrismRA informed treatment selection arm. The Investigator will receive the PrismRA results and use those results to inform treatment selection by Visit 2. Patients may be followed indefinitely from the time of signing the informed consent and medical records release form unless the patient withdraws from the study, dies, or becomes lost to follow-up. Changes to the study biologic and targeted small molecule synthetic disease modifying anti-rheumatic drugs (b/tsDMARDs) do not terminate follow-up following protocol. A patient can withdraw from the study at any time.

External control arm:

The observational external control arm will consist of comparable initiators of b/tsDMARDs in OM1's PremiOM RA dataset, in which the specific choice of tumor necrosis factor inhibitor (TNFi) or non-TNFi b/tsDMARDs was based on the treating physician's clinical judgement and was not informed by the PrismRA test results. Baseline as well as follow-up data will consist of data obtained at routine clinical encounters. The index date (start of follow-up) for this external control arm will be defined as the time of initiation of the study treatment (very first or subsequent b/tsDMARDs) and patients will be followed until week 24, death, or loss to follow-up, whichever occurs first. Changes to the study b/tsDMARDs do not terminate follow-up following protocol. Controls may be sampled from time intervals contemporaneous with the trial (March 2022 and onward) as well as historical periods.

2.0 OBJECTIVES

The objective of the DRIVE study is to establish the clinical utility of the PrismRA test in evaluating therapeutic response for patients with RA.

3.0 STUDY OUTCOMES

In main analyses, binary outcomes measures specified at 12 weeks and 24 weeks below under the Composite Strategy in the ICH E9's estimand framework will be assessed.^[2 3] In the Composite Strategy, a successful outcome will be defined as success achieved at 12 or 24 weeks

and study completed without post-baseline treatment switch during 12 or 24 weeks. In the additional analyses, outcome measures specified at 12 weeks and 24 weeks below will be assessed under the Treatment Policy Strategy. In the Treatment Policy Strategy, any post-baseline treatment switch in the study medication is disregarded.

3.1 Primary Outcome Measure

The proportion of patients with moderate or high disease activity at baseline who achieve a minimal important difference (MID)[4] in CDAI of ≥ 6 (baseline moderate) or ≥ 12 (baseline high) at 24 weeks after study treatment initiation.

The main Composite Strategy analysis examines the proportion of patients with moderate or high disease activity at baseline who achieve a MID[4] in CDAI of ≥ 6 (baseline moderate) or ≥ 12 (baseline high) at 24 weeks after study treatment initiation AND complete study without post-baseline treatment switch. In the additional Treatment Policy Strategy, continuing the study treatment at 24 weeks is not required.

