6.1 Study Type

This is a two-arm, multi-center United States (U.S.)-based study with a prospective, non-blinded intervention arm (PrismRA arm) and an observational external control arm designed to demonstrate the clinical utility of the PrismRA test in routine clinical care. The study will compare outcomes for RA patients with moderate to high disease activity whose treatment is informed by PrismRA test results (PrismRA arm) to outcomes among RA patients who receive the standard of care (SOC) not informed by PrismRA results (external control arm).

PrismRA arm:

In this arm, all patients will receive the PrismRA test. The Investigator will receive the PrismRA results and use those results to inform treatment selection by Visit 2. Patients may be followed indefinitely from the time of signing the informed consent and medical records release form unless the patient withdraws from the study, dies, or becomes lost to follow-up. Changes to the study b/tsDMARDs do not terminate follow-up. A patient can withdraw from the study at any time.

External control arm:

The observational external control arm will consist of comparable initiators of b/tsDMARDs in OM1's PremiOM RA dataset, in which the specific choice of TNFi or non-TNFi b/tsDMARDs was based on the treating physician's clinical judgement and was not informed by the PrismRA test results. Baseline as well as follow-up data will consist of data obtained at routine clinical encounters. The index date (start of follow-up) for this external control arm will be defined as the time of initiation of the study treatment (very first or subsequent b/tsDMARDs) and patients will be followed until week 24, death, or loss to follow-up, whichever occurs first. Changes to the

study b/tsDMARDs do not terminate follow-up. Controls may be sampled from time intervals contemporaneous with the trial (March 2022 and onward) as well as historical periods.

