7.1 Primary Endpoint

The proportion of patients with moderate or high disease activity at baseline who achieve a minimal important difference (MID)¹¹ in CDAI of ≥ 6 (baseline moderate) or ≥ 12 (baseline high) at 24 weeks after study treatment initiation.

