8.11 Patient Withdrawal/Completion

PrismRA arm:

Patients may withdraw from the study at any time without prejudice to their care. The Investigator and/or the Sponsor may withdraw patients at any time who violate the study protocol or, to protect the subject for safety or administrative reasons at any time. It will be documented whether or not each patient completes the determined follow-up visits. Changes to the study treatment during follow-up as indicated by clinical practice does not constitute a protocol violation or withdrawal.

Early withdrawals will include, but are not limited to, those patients who consent to participate in the clinical study but fail to initiate a b/tsDMARD at Visit 2 within 6 weeks of Visit 1.

External control arm:

As existing data from routine clinical care will be utilized, this point does not apply.

9 Safety Assessments

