3.2 Secondary Outcome Measures

Secondary endpoints include the following:

- a) The proportion of patients with moderate or high disease activity at baseline who achieve CDAI ≤ 10 (low disease activity (LDA)) or CDAI ≤ 2.8 (remission) at 12 and 24 weeks after study treatment initiation.
- b) The change in CDAI scores from baseline to 12 and 24 weeks among patients with moderate or high disease activity at baseline who initiate study treatment.
- c) The proportion of patients with moderate or high disease activity at baseline who achieve an MID in CDAI of ≥ 6 and ≥ 12 , respectively, 12 weeks after study treatment initiation.
- d) The proportion of patients with moderate or high disease activity at baseline who achieve a meaningful reduction (defined as ≥ 10 on the scale of 0–100) of patient global assessment (PtGA) compared to the baseline PtGA 12 and 24 weeks after study treatment initiation.
- e) The proportion of patients with moderate or high disease activity at baseline who achieve a minimal clinically important difference (MCID) in RAPID3 (≥ 3.8 on the scale of 0–30)[5] compared to the baseline RAPID3 at 12 and 24 weeks after study treatment initiation.
- f) The proportion of patients with moderate or high disease activity at baseline who achieve an MCID in patient pain visual analogue scale[6] (≥ 1.1 on the scale of 0–10) compared to the baseline pain at 12 and 24 weeks after study treatment initiation.
- g) The proportion of treatment decisions that were guided by PrismRA test results (in the PrismRA arm only).

Proportions for all the binary endpoints assessed at 12 and/or 24 weeks (a, c–f) will be assessed in the Composite Strategy, which will require no post-baseline treatment switch during 12 and 24 weeks, respectively. The additional Treatment Policy Strategy will disregard post-baseline

treatment switch during 12 and 24 weeks for the binary endpoints assessed at 12 and/or 24 weeks (a, c–f).

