3.3 Exploratory Outcome Measures

- a) The proportion of moderate to high disease activity patients that achieve American College of Rheumatology 50% improvement (ACR50) therapeutic response 12 and 24 weeks after study treatment initiation. (In the PrismRA arm only; analysis in the external control arm may only be descriptive in nature if the constructed ACR50 is not sufficiently available in real world data).
- b) The proportion of patients receiving TNFi therapy and non-TNFi b/tsDMARDs as the study treatment at the index date.
- c) The number of patients that stop or change the study treatment due to an intolerance during the 24-week follow-up period (in the PrismRA arm only; analysis in the external control arm will only be a description of any discontinuation or change in the study treatment).

Exploratory Outcome (a) will be assessed in the Composite Strategy, which will require no post-baseline treatment switch during 12 and 24 weeks. In the additional Treatment Policy Strategy, post-baseline treatment switch during 12 and 24 weeks will be disregarded.

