5.0 GENERAL STATISTICAL CONSIDERATIONS

5.1 Sample Size and Power Calculations

The study is powered to detect a difference of 10% in the proportion of patients with improvement in CDAI from baseline to Week 24 by at least the MID as defined in Section 3.1 between the PrismRA arm and the external control arm. Results are shown in **Table 1**. It is estimated that the attrition rate at Week 24 (defined as the proportion of patients with missing CDAI scores at Week 24 for any reason) can be up to 45% in the PrismRA arm and up to 50% in the external control arm. The sample sizes below have been inflated accordingly to account for the patient attrition mentioned above.

With a sample size of 600 in the PrismRA arm and 1,500 in the external control arm, the study has 88% power to establish the superiority of the PrismRA intervention as compared to the standard of care by detecting a difference of 10% between the two study arms based on Fisher’s

exact test of independent proportions assuming the proportion of patients with improvement in CDAI by MID are 40% and 30% in the PrismRA arm and the external control arm, respectively.

Table 1. Study power for comparing proportion of patients with improvement in CDAI from baseline by at least MID between the two study arms

Sample size in the PrismRA arm before attrition	Sample size in the external control arm before attrition	Proportion of patients in the PrismRA arm with MID improvement in CDAI	Proportion of patients in the external control arm with MID improvement in CDAI	PrismRA arm, attrition			
				30%	35%	40%	45%
				Study power			
600	1,000	0.45	0.35	86%	84%	82%	80%
600	1,000	0.40	0.30	87%	86%	84%	82%
600	1,000	0.35	0.25	90%	89%	87%	85%
600	1,500	0.45	0.35	91%	90%	88%	86%
600	1,500	0.40	0.30	92%	91%	89%	88%
600	1,500	0.35	0.25	94%	93%	92%	90%
600	2,000	0.45	0.35	93%	92%	90%	88%
600	2,000	0.40	0.30	95%	93%	92%	90%
600	2,000	0.35	0.25	96%	95%	94%	92%

The sample size calculation was performed with SAS (version 9.4, Cary, NC).

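### The SAP's main primary analysis adds a no-switch condition that Protocol 7.1 lacks, the 88% power is not shown to apply to it, and its completion wording conflicts with the imputation rule

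*SAP*

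**What the plan says.** **Endpoint.** Protocol 7.1 begins "The proportion of patients with moderate or high disease activity at baseline who achieve a minimal important difference (MID" and gives the thresholds (6 points from moderate, 12 from high baseline activity) at 24 weeks. It sets no condition on switching or completion, and the Protocol names no strategy for switches. Protocol 6.1 adds "Changes to the study b/tsDMARDs do not terminate follow-up", and Protocol 8.11 says "Changes to the study treatment during follow-up as indicated by clinical practice does not constitute a protocol violation or withdrawal".

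**SAP strategy.** SAP 3.1 restates the Protocol endpoint and then defines the main (Composite Strategy) analysis as MID "AND complete study without post-baseline treatment switch". SAP 3.0 words it as success "and study completed without post-baseline treatment switch during 12 or 24 weeks". The Treatment Policy version, which disregards switches, is additional. SAP 3.2 drops completion for the binary secondary endpoints and refers only to the Composite Strategy, "which will require no post-baseline treatment switch during 12 and 24 weeks, respectively". SAP 3.3 treats the ACR50 endpoint the same way.

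**Analysis steps.** SAP 6.3.1 runs the outcome models on the imputed datasets for both strategies, but its sentence on what will be reported describes the MID proportion without a switch condition.

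**Power.** Protocol 10.1 and SAP 5.1 both state 88% for MID rates of 40% vs 30%. SAP 5.1 describes the endpoint as improvement "by at least the MID as defined in Section 3.1", a section that holds both definitions.

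**The concern.** A patient who changes drug and has a Week 24 MID is a success under Protocol 7.1 as written and a failure in the SAP's main analysis. The two analyses can give different answers, and the two documents do not state the same primary estimand. The only power figure is built from MID rates, so a reader cannot tell what power the SAP's main analysis has.

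There is also a scoring problem. If the completion wording is taken literally, a drop-out fails. Under the imputation rule, the same drop-out can be a success. Two programmers working from the same SAP could score the primary endpoint differently for that patient, or for one who stops the study drug without starting another.

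**Working it through.** **Step 1: reproduce the stated power.** Inputs from Protocol 10.1 and SAP 5.1: 600 and 1,500 patients before attrition; attrition 45% and 50%; rates 40% and 30%; Fisher's exact test; two-sided alpha 0.05.

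- Evaluable patients: 600 × 0.55 = 330 and 1,500 × 0.50 = 750.
- Exact Fisher power, enumerating both binomials: 88.4%, against the stated 88%.
- All 36 cells of SAP Table 1 reproduce within 2 points in the same way.

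The arithmetic is right. The inputs are MID rates, and no switch rate enters.

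**Step 2: what the composite could do to power.** Let s be the share of MID responders who switch before Week 24. The composite rate is MID rate × (1 − s). The documents give no value of s, so every value below is an assumption. Sample sizes and test are as in Step 1; matching, weights and imputation are ignored.

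| Assumption | PrismRA | Control | Power |
|---|---|---|---|
| No switching (the stated case) | 40% | 30% | 88.4% |
| s = 10% in both arms | 0.40 × 0.90 = 36% | 0.30 × 0.90 = 27% | 83.0% |
| s = 15% in both arms | 0.40 × 0.85 = 34% | 0.30 × 0.85 = 25.5% | 80.0% |
| s = 20% in both arms | 0.40 × 0.80 = 32% | 0.30 × 0.80 = 24% | 76.5% |
| Composite keeps a 10-point gap | 35% | 25% | 90.9% |
| Composite keeps a 10-point gap | 30% | 20% | 93.7% |

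Equal switching shrinks the 10-point gap in proportion, so power falls. Keeping the gap at 35% vs 25% needs somewhat more switching among control responders: 1 − 0.35/0.40 = 12.5% against 1 − 0.25/0.30 = 16.7%. Larger imbalances matter more: s of 10% (PrismRA) and 20% (control) gives 36% vs 24% and 97.7%, while the reverse gives 32% vs 27% and 37.5%. The direction depends on rates that neither document states.

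**Step 3: completion against imputation.**

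- SAP 3.0 and 3.1 require completion and no switch. SAP 3.2 and 3.3 require no switch only.
- SAP 5.4 expects about 45% (PrismRA) and 50% (control) of Week 24 outcomes to be missing, names loss to follow-up among the causes, and imputes missing outcomes under missing at random (MAR).
- SAP 6.3.1 applies those imputed datasets to the composite.

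Read literally, SAP 3.1 fails a drop-out whom SAP 5.4 could score as a success.

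**Step 4: what counts as a switch.** Protocol 8.8 uses the word for a subsequent b/tsDMARD, and SAP 3.0 for a switch in the study medication. SAP 3.1, however, explains Treatment Policy as not requiring continued study treatment. SAP 3.3 keeps stopping and changing apart when it counts patients who "stop or change the study treatment due to an intolerance during the 24-week follow-up period". A patient who stops without a new drug is therefore not clearly classified.

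SAP 5.4 derives binary endpoints from continuous scores, and a CDAI score does not show whether the patient switched. Protocol 8.6 collects current medications and adherence at Weeks 12 and 24, so this last gap concerns only patients without that record.

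**The case against.** The strongest reply is that the SAP does what a SAP should. It repeats the Protocol endpoint, chooses a strategy where the Protocol names none, says clearly which analysis is main, and gives both strategies their own result tables. Protocol 10.4 and 10.5 send analysis detail to the SAP. Most of this stands. What does not follow is that a condition turning Protocol successes into failures is only analytic detail: it changes what is being estimated.

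Three stronger readings are tempting but unsupported.

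- **A reader might infer that the Protocol commits to Treatment Policy and the SAP breaks it.** Continued follow-up after a drug change fits either strategy, and SAP 1.0 carries the same statement alongside the composite. Protocol 8.11 concerns violations and withdrawal, not scoring.
- **A reader might infer that the main analysis is underpowered.** The 40% and 30% are planning assumptions, no switch rate is given, and SAP Table 1 itself shows 90% for 35% vs 25%. Step 2 shows power moving either way.
- **A reader might infer that drop-outs are meant to be failures.** SAP 3.2 and 3.3 suggest that no-switch-only is intended, so this is a wording conflict. No error rate should be attached to the literal reading.

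It is also fair to say that the word switch has some meaning in the documents. Only stopping without a new drug is left open. SAP 5.4 lists the dependent variables in its imputation models, so switch status may partly be covered already.

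**Conclusion.** The mismatch is on the face of the text: Protocol 7.1 has no switch condition, and the SAP's main analysis has one. The 88% is correct for the MID endpoint and is not shown to apply to the composite. Under the assumptions in Step 2, composite power is 83.0% to 76.5% with 10% to 20% equal switching among MID responders, or 90.9% if a 10-point gap holds at 35% vs 25%. These figures show only that the 88% cannot simply be carried over.

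The completion wording contradicts both SAP 3.2/3.3 and the MAR imputation, and the scoring of a stop without a new drug is undecided. Confidence is high for the mismatch and the wording conflict. The effect on power cannot be settled from the documents. The point should be fixed before outcomes are analysed, because it decides which of two candidate results is the primary one.

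**What to change.** (a) Name one primary estimand in both documents. Either keep the Protocol 7.1 MID endpoint under Treatment Policy as primary, attach the 88% to it and make the composite supportive; or amend Protocol 7.1 to the composite and restate the power under stated composite rates or switch rates. Make the reporting sentence in SAP 6.3.1 match the choice.

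(b) Delete the completion wording from SAP 3.0 and 3.1, so that they agree with SAP 3.2, 3.3 and the imputation rule.

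(c) For the composite analysis only, state whether stopping the study drug without a new one counts as a switch when the endpoint is scored. Score an observed switch up to that endpoint's own time point (Week 12 or Week 24) as failure in every imputed dataset. Where switch status is unobserved, impute it within the existing multiple imputation.

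The cost is a few sentences in SAP 3.0, 3.1, 5.4 and 6.3.1, possibly a short Protocol amendment, and slightly more imputation work. If the composite stays primary, the stated power may become less favourable.
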